### **7.7.1.3 Vital Signs**

Vital signs will include height, body weight, BMI, sitting systolic and diastolic blood pressures (BP).

Descriptive statistics (n, mean, SD, median, min, and max) for each vital sign parameter will be used to summarize the observed results and the changes from baseline value by scheduled visit for the Safety Analysis Set.

A listing will be provided for vital signs data for the Included Set.

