6.2. Objectives and Endpoints of the Safety Study Part (Arm 4)

6.2.1. Primary Objective and Endpoints

1. To evaluate the general safety of treatment with E4 20 mg

Safety endpoints for primary objective #1

- 1.1. Frequency of TEAE (including SAEs)
- 1.2. Frequency of changes in results in physical and gynecological examination, vital signs, ECG, mammography, and breast examination at each measured time point
- 1.3. Frequency of changes in routine clinical laboratory tests results (hematology and chemistry) at each measured time point

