9.6.2. Concomitant Medication/Therapy

The use of any concomitant medication taken during the trial will be recorded in the eCRF and will include the name of the drug, treatment regimen (dose, units, frequency, and route of administration), the date of initiation and discontinuation of the therapy, and the indication.

Lipid lowering drugs

If a subject is receiving a lipid-lowering therapy, then her dyslipoproteinemia has to be in line with the exclusion criteria, with $LDL \leq 190$ mg/dL and triglycerides ≤ 300 mg/dL. The subject should be on a stable dose of lipid-lowering therapy for at least 1 month before the start of screening.

Thyroid treatment

Thyroid treatments are allowed as long as the subject has normal TSH levels or low or high TSH levels with normal free T4 at screening.

Treatment for VMS symptoms

Estrogen and/or progestin therapies are not allowed during the trial. A washout period is necessary as described in Section 9.6.1.

The use of non-hormonal medication (prescription medication or OTC) for the treatment of VMS is not allowed in the Efficacy Study part. A washout period is necessary as described in Section 9.6.1. If the medication is used for other indications (e.g., for depressive disorders) then participation is allowed if on a stable dose for at least 3 months prior to the start of screening and no changes in the dose regimen is foreseen during the study period.

To confirm compliance with the rules of unauthorized concomitant therapy, blood samples for the analysis of E2 concentrations will be taken during the treatment visits in the Efficacy Study part.

Antihypertensives

Subjects with mild to moderate hypertension who are controlled on a stable antihypertension regimen may be enrolled if they meet the blood pressure criteria at screening (systolic BP ≤ 130 mmHg, diastolic BP ≤ 80 mmHg). Subjects using methyldopa or clonidine containing antihypertensive medication may not be included in the Efficacy Study part.

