10.4.3. Vital Signs

Vital signs will include height, body weight, BMI, sitting systolic and diastolic BPs, and heart rate. BP will be taken at all visits; height will only be measured during screening, weight will

only be measured at during screening and at the EoT visit. The same equipment (e.g., scale) should be used for all measurements. BMI will be calculated from the subjects height and weight using the formula $BMI = \text{kg}/\text{m}^2$; where kg is the body weight in kilograms and m^2 is the body height in meters squared. BP measurements will be made using a sphygmomanometer with an appropriate cuff size for the individual subject. Measurements will be taken while the subject is seated after at least 5 minutes at rest. Other procedures should not be performed during the time of the blood pressure and pulse rate measurements. BP measurements at screening may be repeated if values are outside the inclusion criteria after sitting for an additional 5 to 10 minutes. The last reading will be used for eligibility.

All abnormal findings in vital signs that are considered by the Investigator to be clinically significant will be recorded as AEs (Section 10.4.1).

10.4.4. **Electrocardiogram**

A 12-lead ECG will be recorded for each subject during screening and at the EoT Visit (Visit 7 Efficacy Study part/Visit 6 Safety Study part). ECGs will be read locally. The ECG interpretation scheme will include the analysis of the morphology, rhythm, conduction, ST segment, PR, QRS, QT and QTc (according to QTcFrid) intervals, T waves, U waves and the presence or absence of any pathological changes.

All abnormal findings in ECG that are considered by the Investigator to be clinically significant will be recorded as AEs (Section 10.4.1).

10.4.5. **Routine Clinical Laboratory Tests**

Methods for blood collection, processing, and shipment are described in instructional materials provided to investigational sites. Leftover blood samples will be retained after this trial for optional additional analyses in the context of this program or any further research on E4; details of the sample retention for future research as well as subject's rights in regard to these samples are presented in the ICF.

Blood samples for the assessments lipids and glucose need to be taken in **fasting** conditions (at least 8 hours fast).

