## **2 STUDY OBJECTIVES AND ENDPOINTS**

### **2.1 Primary Objective and Endpoint**

To evaluate the general safety of treatment with Estetrol (E4) 20 mg.

Safety endpoints for primary objective #1

- Frequency of Treatment Emergent Adverse Event (TEAE) (including Serious Adverse Events [SAEs])
- Frequency of changes in results in physical and gynecological examinations, vital signs, electrocardiogram (ECG), mammography, and breast examination at each measured time point
- Frequency of changes in routine clinical laboratory tests results (hematology and chemistry) at each measured time point

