### **7.7 Safety Analyses**

The safety evaluations will include analyses of TEAEs, physical and gynecological examination, breast examination, vital signs, ECG, routine clinical laboratory tests and mammography. For all safety endpoints, visits will be clustered as specified in [Table 6](#) and [Table 7](#) of Appendix 1.

The safety analyses involving changes from baseline to a specific time point for safety variables (e.g., laboratory parameters, vital signs, and ECG) will only include subjects from the Safety Analysis Set who have data available for both the baseline and the time point under consideration unless otherwise specified.

All safety evaluations will be summarized using data from the Safety Analysis Set if not indicated otherwise. No formal statistical test will be performed. Continuous variables will be summarized using descriptive statistics (n, mean, SD, median, min, max), categorical variables will be presented in frequency tables using counts and percentages.

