- e) Blood pressure, heart rate, body height (during screening only) and body weight (during screening and EoT only).
- f) To be performed in subjects with uterus and/or cervix, unless a written normal result is available within 18 months before screening start. The PAP test may be repeated once in case of inadequate or insufficient sample.
- g) Unless a written normal result, including digital imaging, is available within 9 months before screening start.
- h) Mammography at EoT visit may only be performed if the subject was treated for at least 12 weeks and the last mammography was taken at least 9 months earlier.
- i) If the subject is not fasting, a new appointment needs to be made as soon as possible. Laboratory tests may be repeated once during the screening period, at the discretion of the investigator.
- j) Additional blood samples, including one DNA sample at Visit 1 only, will be collected for optional additional analysis of in the context of this program or any further research on E4.
- k) A pregnancy test may be performed at the discretion of the Investigator.
- l) TVUS at screening and EoT will be taken for all subjects who still have a uterus and/or ovaries. At all other time points a TVUS will be performed to monitor the endometrium thickness only for subjects who still have a uterus.
- m) Visit 7 for non-hysterectomized subjects only at approximately 10 days after completion of the progestin treatment.
- n) Non-hysterectomized subjects only.
- o) If the subject was treated for at least 12 weeks.
- p) Subjects are instructed during screening on how to fill in the diary and if needed can be re instructed.
- q) At each visit the diary will be checked. Completed pages will be collected and will remain at the study site.
- r) Progestin treatment for non-hysterectomized subjects only.
- s) If lipid and/or glucose parameters could be a reason of concern in the judgement of the Investigator, fasted blood sampling for lipid and glucose parameters assessment may be done during the Washout Visit. Otherwise, this assessment will be done during the Screening Period.
- t) Laboratory tests may be repeated once during the screening period, at the discretion of the investigator. FSH measurement is not required for subjects with bilateral oophorectomy.
- u) In the event screening requirements cannot be met within 4 weeks, the screening period may be extended with prior Medical Monitor approval, but screening period may not exceed 8 weeks.

---

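### No planned table gives the frequency of changes in vital signs, one component of a primary safety endpoint of the Safety part, and heart rate is missing from the SAP's vital signs analysis

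*SAP*

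**What the plan says.** **Endpoint.** Protocol 6.2.1, endpoint 1.2, reads "Frequency of changes in results in physical and gynecological examination, vital signs, ECG, mammography, and breast examination at each measured time point". SAP 2.1 repeats it: "Frequency of changes in results in physical and gynecological examinations, vital signs, electrocardiogram (ECG), mammography, and breast examination at each measured time point". It is the second of three safety endpoints under the primary objective. The first is treatment-emergent adverse events and the third is routine laboratory tests.

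**Parameters.** Protocol 10.4.3: "Vital signs will include height, body weight, BMI, sitting systolic and diastolic BPs, and heart rate". SAP Appendix 2, footnote e: "Blood pressure, heart rate, body height (during screening only) and body weight (during screening and EoT only". SAP 7.7.1.3 gives the same list as the protocol but stops at blood pressure: "Vital signs will include height, body weight, BMI, sitting systolic and diastolic blood pressures (BP".

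**Planned output.** SAP 7.7.1.3: "Descriptive statistics (n, mean, SD, median, min, and max) for each vital sign parameter will be used to summarize the observed results", together with the changes from baseline, by scheduled visit, plus a listing. The general rule in SAP 7.7 is that "categorical variables will be presented in frequency tables using counts and percentages", but no categorical vital sign variable is defined anywhere in the SAP.

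**Departures.** SAP section 8 lists three changes from the protocol, all about analysis sets. Neither the vital signs output nor heart rate is among them.

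**The concern.** A frequency of changes is a number and percentage of women who changed in some defined way. A mean change, even with its SD, median and range, is a different quantity and does not give that number. For this component the SAP states one endpoint and plans the summary of another.

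Blood pressure is where the difference matters most. Protocol 5.4 says hypertension has been induced or made worse in users of menopausal hormone therapy, and in the same sentence that such therapy usually goes with lower blood pressure. Falls in many women and rises in a few can offset each other in a mean. The count of women who rose is then the informative figure.

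The part is open label, so categories chosen after the data are seen would carry little weight. They need to be fixed in advance.

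**Working it through.** The plan states no figure here to reproduce. The check is a comparison of the endpoint with the planned output, followed by a calculation on one possible remedy.

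**1. Components of endpoint 1.2 against SAP output**

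| Component | SAP section | Shift table planned |
|---|---|---|
| Physical examination | 7.7.1.4 | yes |
| Gynecological examination | 7.7.1.7 | yes |
| Vital signs | 7.7.1.3 | **no** |
| ECG | 7.7.1.5 | yes |
| Mammography | 7.7.1.9 | yes |
| Breast examination | 7.7.1.8 | yes |

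Five of six components are covered. Laboratory tests (7.7.1.2) are continuous, as blood pressure is, and get both descriptive statistics and a low/normal/high shift table.

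**2. Parameters.** Protocol 10.4.3 has six: height, weight, BMI, systolic BP, diastolic BP and heart rate. SAP 7.7.1.3 has the first five.

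**3. What a mean can show.** Suppose 5% of 400 women rise by 20 mmHg and the rest do not change. The mean moves by 0.05 × 20 = 1.0 mmHg (0.4 for 2%, 2.0 for 10%). All 400 women rising by 1 mmHg gives the same mean. With an assumed SD of change of 10 mmHg, the SE is 10/√400 = 0.5. With the roughly 200 completers expected at 12 months (protocol 8.1), it is 10/√200 = 0.71.

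**4. Would the screening limits serve as categories?** Protocol 9.6.2 gives "systolic BP ≤ 130 mmHg, diastolic BP ≤ 80 mmHg" as the blood pressure criteria at screening. SAP Table 1 takes baseline as the last value before the Treatment Start Date, and protocol 10.1.6.1 has treatment start on the day of Visit 1. Read literally, baseline is then usually a screening value already selected to be at or below the limits. A shift table at 130/80 would have almost one populated baseline row.

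To see what selection alone does, assume no drug effect. Let unselected systolic BP be normal with mean μ of 118 to 122 and SD σ of 10 to 12 mmHg, and let any two visits have correlation ρ of 0.6 to 0.8. None of these values is in the documents. With z = (130 − μ)/σ, the share above 130 mmHg at one later visit, given screening at or below 130, is 1 − Φ₂(z, z; ρ)/Φ(z).

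- Low end (μ 118, σ 10, ρ 0.8): z = 1.2, and 1 − 0.8363/0.8849 = 5.5%.
- High end (μ 122, σ 12, ρ 0.6): z = 0.667, and 1 − 0.6314/0.7475 = 15.5%.

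Simulating the five on-treatment visits (Visits 2 to 6) under the same assumptions gives 15% to 41% of women above 130 mmHg at least once.

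**5. Are change categories free of this?** Not entirely. The expected change after selection is (1 − ρ)·σ·φ(z)/Φ(z).

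- Low end: 0.2 × 10 × 0.1942/0.8849 = 0.4 mmHg.
- High end: 0.4 × 12 × 0.3194/0.7475 = 2.1 mmHg.

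This upward drift affects the planned means as well. Change categories do not count crossings of the selection limit itself, and showing rises and falls side by side keeps the drift visible.

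**The case against.** The strongest reply is that protocol 12.8 itself prescribes these descriptive statistics for continuous safety variables and frequency tables for categorical ones. On that view SAP 7.7.1.3 does what the statistics section asks, and the fault is an endpoint term never defined for vital signs. Laboratory tests have reference ranges and examinations have an investigator's status; vital signs have neither. This stands as an account of how the gap arose. It does not close it, because both documents still name a frequency as the endpoint.

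A second reply is that clinically significant abnormal vital signs are recorded as adverse events (protocol 10.4.3) and counted there, and that all subject data are listed (SAP 7.1). So a reader should not infer that an important rise in blood pressure would go unreported, or that heart rate is lost: it can still appear in a listing. But the adverse event tables serve endpoint 1.1 and cover only what the investigator judges significant, and a listing is not a frequency.

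A reader might also infer that a rise in a minority of women would be hidden by the planned summary. That goes too far. In the example above, 1.0 mmHg is two SEs at n = 400 under the assumed SD, and the planned maximum shows the largest rise. The summary cannot show how many women rose.

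Finally, a reader might think the protocol already supplies the cut-off at 130/80 mmHg. It does not. Those are eligibility limits, with a repeat reading allowed and the last one counted (protocol 8.2.2, footnote 17), and not limits of abnormality or of change.

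**Conclusion.** The point holds in a limited form. For one of six components of the second of three primary safety endpoints, no planned table gives the required frequency, and one of six vital sign parameters has no planned summary. Section 8 of the SAP explains neither, and shift tables for every other component suggest an oversight.

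It would be wrong to conclude that the primary endpoint as a whole goes unanalyzed, or that only means and SDs are planned: median, range, changes from baseline and a listing are there too. No test or confidence interval depends on this, so the consequence is an incomplete primary safety report. It should be corrected before database lock.

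The comparison of sections needs no assumption. The 6% to 16% and 15% to 41% figures depend on the assumed means, SDs and correlations, on normality, and on baseline being a screening value. They bear on the choice of remedy, not on whether the gap exists.

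**What to change.** In SAP 7.7.1.3:

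- Add heart rate to the parameters.
- Add, at each visit, the number and percentage of women in change categories for systolic BP, diastolic BP and heart rate, fixed before database lock. Bands for the size of increase and of decrease from baseline would do, since they do not reuse the eligibility limit. State which reading is baseline: protocol 12.2 uses the last value before the first dose, which could admit a pre-dose Visit 1 reading, whereas SAP Table 1 uses the last value before the start date.
- If counts above 130/80 mmHg are also shown, label them as descriptive counts against the screening limit. Note that selection at screening alone would put a sizeable share above it later, with no control arm in this part. Omit a count of women above the limit at any visit, or give it only with that note.

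If the sponsor prefers not to tabulate frequencies, it should record and justify the departure in SAP section 8.

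The cost is one extra table and one more parameter, from data already collected. The drawback is that the categories are a convention and the counts have no comparator, so they describe and do not attribute.

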### **7.7.1.4 Physical Examinations**

Physical examination results will be summarized by frequency counts (n) and percentages for each body system at baseline and post-dose scheduled visit for the Safety Analysis Set.

A shift table will be produced to summarize change in the frequency counts (n) and percentages of subjects with normal, abnormal without clinical significance, and abnormal with clinical significance from baseline to post-dose scheduled visits for the Safety Analysis Set.

A listing will be provided for physical examination data for the Included Set.

### **7.7.1.5 Electrocardiograms**

Only ECG status (normal, abnormal non clinically significant, abnormal clinically significant) will be collected in the CRF.

A shift table will be produced to summarize the change in the frequency counts (n) and percentages of subjects with normal, abnormal without clinical significance, and abnormal with clinical significance from baseline to post-dose scheduled visits for the Safety Analysis Set.

A listing will be provided for ECG data for the Included Set.

### **7.7.1.6 Other Safety Assessments**

### **7.7.1.7 Gynecological Examinations**

Gynecological examination results will be summarized by frequency counts (n) and percentages for each body system at baseline and post-dose scheduled visits for the Safety Analysis Set.

A shift table will be produced to summarize change in frequency counts (n) and percentages of subjects with normal, abnormal without clinical significance, and abnormal with clinical significance from baseline to post-dose scheduled visits for the Safety Analysis Set.

A listing will be provided for gynecological examination data for the Included Set.

### **7.7.1.8 Breast Examinations**

Breast examination results will be summarized by frequency counts (n) and percentages for each body system at baseline and post-dose scheduled visits for the Safety Analysis Set.

---

A shift table will be produced to summarize change in frequency counts (n) and percentages of subjects with normal, abnormal without clinical significance, and abnormal with clinical significance from baseline to post-dose scheduled visits for the Safety Analysis Set.

A listing will be provided for breast examination data for the Included Set.

#### **7.7.1.9 Mammography**

Subjects must have a Breast Imaging-Reporting and Data System (BI-RADS) score of 1 or 2 to enroll in the study.

A shift table will be produced to summarize change in frequency counts (n) and percentages of subjects BI-RADS score from baseline to EoT visit for the Safety Analysis Set.

A listing will be provided for mammography data for the Included Set.

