10.4.6. Mammography

A digitalized mammogram will be performed during the Screening period unless a written report, preferably with digital imaging, demonstrating a normal result is available within 9 months before the Screening visit. Subjects must have a Breast Imaging-Reporting And Data System (BI-RADS) score of 1 or 2 to enroll in the study. An incomplete mammogram result, i.e., BI-RADS 0, is not acceptable and requires further assessment. The site must obtain a copy of the official report for the subject's study file, including the digital imaging if available.

An additional digitalized mammography will be performed at the EoT (Visit 7 Efficacy Study part/Visit 6 Safety Study part) or at early termination. In case of early termination, mammography may only be performed if the subject was treated for at least 12 weeks and the last mammography was taken at least 9 months earlier.

The mammogram will be used for exploratory evaluation of the change from baseline to EoT in breast density in subjects who have a paired digitalized mammography.

More information is to be found in the Imaging Manual.

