## **3 STUDY DESIGN**

### **3.1 General Study Design**

This study is a Phase III study, with multiple centers in the USA and Canada. Eligible subjects will be post-menopausal women,  $\geq 40$  up to  $\leq 65$  years of age, seeking treatment for relief of moderate to severe vasomotor symptoms (VMS) associated with menopause.

The Safety Study part will be conducted in approximately 200 hysterectomized and approximately 200 non-hysterectomized postmenopausal women, who are seeking treatment for the relief of VMS (condition clinically indicated by the investigator) associated with menopause and have at least 1 moderate to severe VMS symptom per week.

The Safety Study part is an open label study, to evaluate the effect of E4 20 mg (Arm 4) on the primary safety and secondary efficacy endpoints (lipid and glucose metabolism, HRQoL and TS) over a 52 week treatment period. For endometrial protection, all non-hysterectomized subjects will receive treatment with 200 mg progesterone (P4) once daily for 14 consecutive days, after completion of the E4 treatment. The target number of subjects to be included in the Safety Study part is approximately 400. Enrollment in the Safety Study part will stop as soon as the minimum required number of subjects in each study group and study part is enrolled.

[figure not shown]
At least 8 visits (up to 15 months) are planned in the Safety Study part, this includes:

- Washout visit (occurring generally up to 8 weeks prior to Screening visit),
- Screening visit (occurring 4 weeks prior to Baseline [Visit 1]),
- Treatment visits (occurring within 53 weeks; Visit 1 to Visit 6), include:
  - Baseline (Visit 1),
  - Five On-treatment visits (Visits 2, 3, 4, 5 and 6), the last treatment visit (Visit 6) is also the end of treatment (EoT) visit, which will also occur in case of early discontinuation.

For non-hysterectomized women an additional endometrial safety follow-up visit (visit 7) is planned approximately 10 days after completion of the 14 days of P4 treatment, which will also occur in case of early discontinuation

The trial schedule for Safety Study part is summarized in [Figure 1](#).

Figure 1: Trial Schedule

EoT = End of Treatment; NH = Non-hysterectomized; H = Hysterectomized; E4 = estetrol; P4 = progesterone

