## 7 STATISTICAL METHODS

### 7.1 General Statistical Conventions

All statistical procedures will be completed using SAS version 9.4 or higher, there is only one treatment group, thus no formal statistical analysis will be performed.

Confidence intervals (CIs) will be presented as 2-sided 95% CIs unless specified differently in specific analysis.

Categorical variables will be summarized using frequency counts (n) and percentages in each category, percentages will be computed for subjects with non-missing value (as the denominator). If there are missing values, missing values counts will be provided. All percentages will be rounded to one digit after decimal point. The frequency counts and percentages will be presented in the form XX (XX.X %), where the percentage is in the parentheses. If the percentage of a category is '100 %', then it will be displayed as '100 %' (no decimals will be added after 100).

Continuous variables will be summarized using the number of subjects with non-missing values (n), mean, median, standard deviation (SD), minimum (min), maximum (max) and missing values counts. Missing values counts will be displayed only if there are missing values. All mean and median values will be formatted to one more decimal place than the measured value. Standard deviations will be formatted to two more decimal places than the measured value. The min and max will be displayed to the same number of decimal places as the measured value. Unscheduled visits will not be summarized in tables.

Analyses will be performed by visit, irrespective of any time window deviations, unless otherwise specified. The early discontinuation (ED) visit will be separated from the scheduled EoT- visit based on discontinuation reason. Unscheduled visits related to efficacy data will be clustered with scheduled visits based on the visit windows in [Table 5](#) of Appendix 1. Similarly, the unscheduled visit results will be clustered with scheduled visits based on the visit windows defined in [Table 6](#) (Appendix 1) for microscopic findings and laboratory endpoints and endometrial biopsy. Similarly, the scheduled visits for ECG, Procedures, Questionnaire, Vital Signs, Imaging and Findings will be based on visit window [Table 7](#) in Appendix 1.

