**Table 7: Visit Window ECG, Procedures, Questionnaire, Vital Signs, Imaging and Findings**

Assessment Visit	Time window	Visit
Safety Visit 2		Week 5
Safety Visit 3		Week 13
Safety Visit 4		Week 29
Safety Visit 5		Week 41
Safety Visit 6/EoT		Week 53 (if discontinuation reason is missing in DS domain) Early Discontinuation (if discontinuation reason is non-missing in DS domain)
Safety Visit 7 Follow-up		Week 55/56 Follow-up

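### The Safety part's mammography shift table has no place for a BI-RADS worsening found on an unscheduled film, and the SAP does not settle how early-discontinuation films are shown

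*SAP*

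**What the plan says.** - SAP 2.1 makes the frequency of change in mammography, at each time point measured, part of the Safety part's primary safety endpoint.
- SAP 7.7.1.9 requires a BI-RADS score of 1 or 2 at entry. It then plans one table: "A shift table will be produced to summarize change in frequency counts (n) and percentages of subjects BI-RADS score from baseline to EoT visit", on the Safety Analysis Set. A listing on the Included Set accompanies it.
- SAP 7.1 sets the visit conventions. On unscheduled data: "Unscheduled visits will not be summarized in tables". On early leavers: "The early discontinuation (ED) visit will be separated from the scheduled EoT- visit based on discontinuation reason". On imaging: "the scheduled visits for ECG, Procedures, Questionnaire, Vital Signs, Imaging and Findings will be based on visit window" Table 7.
- Table 7 lists scheduled Visits 2 to 7 only. Its Visit 6/EoT row is labelled Week 53 or Early Discontinuation, depending on whether a discontinuation reason is recorded. Table 6, for laboratory and microscopic findings, does have windows for unscheduled results.
- SAP 3.1 uses the term more broadly: "the last treatment visit (Visit 6) is also the end of treatment (EoT) visit, which will also occur in case of early discontinuation".
- Protocol 10.4.6 limits exit films: "In case of early termination, mammography may only be performed if the subject was treated for at least 12 weeks" and the last film is at least nine months old. Footnote h of the schedule (Protocol 2.2 and SAP Appendix 2) attaches the same two conditions to the EoT visit in general.

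**The concern.** Every woman enters with a BI-RADS score of 1 or 2, so the main use of the table is to show moves to a worse score. Two kinds of film may fall outside it.

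The first is an unscheduled on-treatment film, for example one taken to follow up a breast symptom. No mammogram is scheduled between baseline and Visit 6, so imaging that itself leads to stopping treatment would ordinarily be of this kind. The second is the exit film of a woman who leaves early, if EoT visit in 7.7.1.9 is taken in the narrow sense of 7.1.

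The endpoint is a frequency. A film that appears only in a listing does not contribute to it, so a worsening seen only on such a film makes the tabulated frequency too low.

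**Working it through.** **A. Following an unscheduled film through the SAP**

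1. The table ends at the EoT visit (7.7.1.9).
2. Section 7.1 bars unscheduled visits from tables. It makes exceptions by assigning unscheduled efficacy results to visits through Table 5, and unscheduled laboratory and biopsy results through Table 6. Imaging goes to Table 7, which offers no such assignment.
3. A later exit film is generally ruled out. Take nine months as 274 days (an assumption). Visit 6 falls on Days 365 to 371. Since 365 − 274 = 91 and 371 − 274 = 97, footnote h bars an exit film at Visit 6 after any unscheduled film later than Day 91 to 97, depending on the visit day. A woman who stops within 274 days of an unscheduled film is barred at her early-discontinuation visit.
4. I say generally because Protocol 10.4.6 and 10.1.6.6 state the nine-month condition for early termination only, whereas footnote h states it for the EoT visit as a whole. These passages should be reconciled. Even if a completer does have an exit film, the table shows her score at that visit and not the worsening found before it.
5. Elsewhere the SAP makes room for such data. Laboratory and lipid/glucose summaries use the last value whether scheduled or not (7.7.1.2, 7.6.1.5). The consensus biopsy diagnosis has a worst-case analysis that includes unscheduled visits (7.7.1.12.2).

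**B. What EoT visit means for early leavers**

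- Narrow sense: 7.1 separates the early-discontinuation visit from the scheduled EoT visit, and Table 7 gives it another label.
- Broad sense: 3.1 says the EoT visit also takes place at early discontinuation. The Appendix 2 schedule puts the mammogram in a single column for EoT and early discontinuation. Footnote h attaches a 12-week treatment condition to the EoT mammogram, and that condition can only bind a woman who leaves early. Table 7 keeps both labels under one Visit 6/EoT row.

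The broad sense has the better support, but the text does not say whether the two labels are pooled, shown apart or reduced to Week 53.

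**C. How many exit films depend on the answer**

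The plan's own figure comes first. Protocol 8.1 expects about 400 women and 50% dropout: 400 × (1 − 0.50) = 200 completers, as stated, and so 200 early leavers.

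Earliest day for an exit film = max(84, 274 − days from last film to Day 1). If dropout is uniform over 364 days and every eligible woman is imaged (both assumptions), the number eligible is 200 × (364 − earliest day)/364.

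| Last film before Day 1 | Earliest day | Eligible of 200 |
|---|---|---|
| 9 months before a 4-week screening | 84 | 154 |
| Start of an 8-week screening | 218 | 80 |
| Start of a 4-week screening | 246 | 65 |
| Day before Day 1 | 273 | 50 |

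Exit films would then be 50/(200 + 50) = 20% to 154/(200 + 154) = 44% of all post-baseline films, if all 200 completers are imaged. The other 46 to 150 early leavers would have no exit film under the protocol, however the table is drawn.

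**The case against.** The strongest reply is that nothing in 7.7.1.9 excludes early leavers. The broad sense of EoT visit is the SAP's own, and footnote h uses it for mammography in particular. Separating two visits is not the same as dropping one, and the table shells, which might settle the display, are in a separate document. That stands: for early-discontinuation films the fault is ambiguity, not omission.

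The contrast with the ECG and physical examination shifts, which run to post-dose scheduled visits, adds little. Those assessments also have a single scheduled post-dose time point.

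A reader might infer that women who stop early drop out of the primary safety endpoint. The documents do not support this. These women remain in the adverse event tables, including events leading to discontinuation, in the breast-examination shift table and in the full mammography listing. Many have no exit film because of the protocol's conditions and not because of a SAP rule. A reader might also attach a size to a downward bias by assuming worsening rates for completers and leavers. The documents give no such rates, and no number of women expected to stop for a breast finding.

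It can also be said that keeping unscheduled visits out of tables is a general convention and that the analysis is single-arm and descriptive. Both are true. But the convention is relaxed for laboratory and biopsy data, and a listing does not supply a frequency. The adverse event route is only partial: Protocol 10.4.2 to 10.4.4 say that clinically significant examination, vital-sign and ECG findings are recorded as adverse events, while 10.4.6 has no such sentence for mammography and relies on the general definition.

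**Conclusion.** The point about unscheduled films holds on either reading of EoT visit. A BI-RADS worsening found that way is not counted in the only mammography table, and the woman will generally have no exit film through which to enter it. The effect on the reported frequency can only be downward, but it cannot be sized because neither the number of unscheduled films nor a worsening rate is given.

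The point about early discontinuation is an ambiguity that should be closed. Roughly 50 to 154 exit films could be affected, on the assumptions of uniform dropout, full imaging of eligible women and the film ages tabulated above. The loss, if any, is from one summary table and not from the safety evaluation as a whole. No formal test or decision threshold depends on it. The change is still worth making, because mammography is a named component of the primary safety endpoint and the remedy is cheap.

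**What to change.** In SAP 7.7.1.9:

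- Present the BI-RADS shift from baseline to Week 53 and, separately, from baseline to Early Discontinuation, using the Table 7 labels.
- Add a panel from baseline to the worst post-baseline BI-RADS score on any mammogram, including unscheduled ones. Use women with any post-baseline mammogram as the denominator, and report how many women in the Safety Analysis Set have none. State where a score of 0, which the protocol treats as incomplete, falls in the ordering.
- Say that the panel is an exception to the 7.1 rule on unscheduled visits.

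The cost is a few sentences of SAP text, one extra panel and one stated exception. No imaging, visit or data collection changes. The added panel cannot help women who have no post-baseline film, which is why their number should be shown.
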